5. TREATMENT OF SUBJECTS

5.1 Investigational product/treatment

The investigational products in this study are two different types of bread, *i.e.* gluten-free oat bread and gluten-containing oat bread. Oat itself does not contain gluten. This gluten-free oat bread is commercially available at the Dutch supermarket "Jumbo", the bread is called "Yam" and made from 100% food-grade ingredients suitable for human consumption. The gluten-containing oat-bread is the same bread, but with the addition of 9.3% gluten (*i.e.* ~4 g per slice, resulting in a minimal intake of 16g per day). No improvers, preservatives, sweeteners, flavours and no colours from artificial sources will be used in this bread recipe. Both breads are similar with regard to texture, taste and appearance and will be baked, labelled and provided in kind by the European Bakery Innovation Centre, Papendrecht, The Netherlands. For more information on the nutritional value of the product, see section 6.1.

5.2 Use of co-intervention (if applicable)

Volunteers reporting a gluten-free or gluten-restricting diet should have been on this for at least one week prior to the study and continue with this throughout the study. To minimalize the influence of altered food and beverage intake on outcome parameters during the study period, the test day will take place at the MUMC+, Amsterdam UMC or WUR in a controlled setting under supervision of the researcher. If part of the test day is carried out outside these study sites, the participants will be given clear instructions on the (un)allowed intake and will be asked to record their beverage intake during the day. Subsequently, we will ask participants to maintain their dietary habits (or the gluten-free/gluten-restricted diet they started prior to the study) as much as possible during the follow-up period. There will be no further dietary restrictions, apart from the test day. During the test day, the participants are free to do what they want to (watching TV, reading, working, possibly take a walk), provided they complete the questionnaires every hour.

5.3 Escape medication (if applicable)

We do not expect that the use of escape medication will be necessary. However, participants are permitted to use paracetamol if necessary. The use of nonsteroidal anti-inflammatory drugs (NSAIDs) and opioids are not allowed during the test day. The number of tablets, dose, and the reason for the medication use have to be reported in the electronic diary. If paracetamol does not work adequately and participants experience intolerable symptoms during the study, the involved gastroenterologists in this study ([name]) will advise on whether or not to stop the intervention. In that case, VAS-scores for the remaining questionnaires were replenished using the highest VAS-score achieved thus far.

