6.4 Summary of known and potential risks and benefits

The study oat breads are commercially available. Bread itself is a harmless food product, which is widely consumed on a daily basis by the general population worldwide. The volunteers may or may not experience mild GI symptoms after the consumption of the study bread, since the included participants suffer from self-reported gluten sensitivity. It should be noted that the consumption of gluten by non-coeliac gluten sensitive participants does not lead to coeliac-specific antibodies and villous atrophy or any allergy related processes (21). Typically, symptoms improve or disappear shortly (mostly within hours) after gluten is withdrawn from the diet (14, 22). The provided study breads contain no more gluten than is present in normal commercially available bread (9.3%) consuming 4 slices of the study bread will not exceed the average amount of gluten that is normally consumed per day (23). Participating in this study does not lead to direct benefits for the individual participants, but may give the participants some insights into the effects of gluten and wheat on their symptoms and well-being. The results of this study will be used to better understand why some types of bread can lead to certain symptoms and who is most vulnerable to experience these symptoms.

Although the risk of consuming gluten for 1 day is considered to be very low, we still would like to limit any potential risk by excluding participants with coeliac disease. Furthermore, the inclusion of such patients may lead to a bias in the study and the expected effects. Therefore, volunteers will only be eligible when coeliac disease is ruled out by means of serologic examination or previous upper GI endoscopy. Participants reporting wheat allergy during the screening visit will also be excluded.

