7. METHODS

7.1 Study parameters/endpoints

7.1.1 Main study parameter/endpoint

Overall symptom score in the short term (within 8 hours)

The primary outcome is the overall GI symptom score after manipulation of information giving a certain expectation about the bread treatment. Overall (GI) symptom score will be measured using VAS (0 to 100 mm) anchored at the low end (score of 0) with the absence of overalls symptoms and at the other end with extreme of severity of symptoms, the worst it has ever been (score of 100) (see also addendum "F2_Klachtendagboek_WoWstudy_ Versie1.0_05-03-2018"). A relevant change is defined as at least a 15 mm increase in self-reported overall symptoms compared with baseline.

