7.5 Replacement of individual subjects after withdrawal

We do not expect dropouts, because the study is not very burdensome in a physical way and so, is not very difficult to complete. When participants withdrawn from the study after signing informed consent but prior to the test day, or prove to be unsuitable on the basis of the screening and therefore cannot participate in the study, an alternative candidate may be selected, in order to ultimately meet the calculated sample size/power. If participants withdraw from the study before the test day, these results will be destroyed immediately after completion of the study.

When participants withdrawn from the study at the test day (*i.e.* after randomisation), before or after receiving and consuming the study breads because of intolerable symptoms, there will be no replacement of participants. These participants are included in the intention-to-treat analysis, because this is seen as important regarding tolerance of the intervention. In that case, missing VAS-scores for the remaining days of the study period will be imputed with the last observation carried forward.

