7.6 Follow-up of subjects withdrawn from treatment

After withdrawal, no follow-up of participants will take place. In case of withdrawal due to medical complications, participants will be referred to a general physician.

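### Sections 5.3 and 7.5 give different fill-in rules for VAS scores after intolerable symptoms, so some participants can be scored in two ways

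*Protocol*

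**What the plan says.** Section 5.3 deals with symptoms that escape medication does not control: "If paracetamol does not work adequately and participants experience intolerable symptoms during the study", the study gastroenterologists advise on whether to stop the intervention. In that case "VAS-scores for the remaining questionnaires were replenished using the highest VAS-score achieved thus far".

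Section 7.5 deals with participants who withdraw on the test day after randomisation, "before or after receiving and consuming the study breads because of intolerable symptoms, there will be no replacement of participants". It keeps them in the analysis: "These participants are included in the intention-to-treat analysis, because this is seen as important regarding tolerance of the intervention". It then states that "missing VAS-scores for the remaining days of the study period will be imputed with the last observation carried forward".

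Section 7.6 adds: "After withdrawal, no follow-up of participants will take place". Section 7.1.1 defines the endpoint, within 8 hours: "The primary outcome is the overall GI symptom score after manipulation of information giving a certain expectation about the bread treatment". Section 3.2 schedules VAS ratings at baseline and hourly on the test day, and section 3.3 adds end-of-day questionnaires on days 1, 2 and 3. Section 9 asks for intention-to-treat analysis of all outcomes but does not say how missing scores are filled.

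**The concern.** The protocol fixes two single-value imputation rules for overlapping events, and neither section refers to the other. This is a contradiction in stated text, not a detail left for a later analysis plan.

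The affected participants carry weight. They are not replaced, and the 5% allowance in section 4.4 covers only drop-out for other reasons. Their filled-in scores therefore enter a comparison planned at 20 per arm. They are also the people who reacted most strongly, and if expectancy works as hypothesised they may be unevenly spread over the arms. Under section 7.2 the investigator knows the expectancy arm, which is the primary contrast, so blinding to the bread does not protect a late choice between the rules.

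A second weakness is common to both rules. Section 3 includes the two follow-up days partly to watch symptoms disappear, and section 6.4 expects that "symptoms improve or disappear shortly (mostly within hours) after gluten is withdrawn from the diet". Filling days 2 and 3 with a constant taken from the test day removes that information.

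**Working it through.** **1. The two rules side by side**

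| | Section 5.3 | Section 7.5 |
|---|---|---|
| Trigger | Intervention stopped for intolerable symptoms not controlled by paracetamol, on medical advice | Withdrawal from the study on the test day for intolerable symptoms |
| Value filled in | Highest VAS so far | Last VAS observed |
| Time points | All questionnaires still to come | Days left in the study period |
| Limited to missing scores? | Not stated | Yes |

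The triggers are not the same, but a participant who stops the bread and leaves on the test day satisfies both.

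**2. Which outcomes are reached**

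- Day 2 and day 3 questionnaires: both rules cover them, so the conflict is direct.
- Hourly test-day scores, if the days left include the rest of day 1: both rules cover them, and the primary outcome is affected.
- Hourly test-day scores, if they do not: section 7.5 keeps the participant in the intention-to-treat analysis with no rule of its own for those hours. Section 5.3 helps only if its trigger was also met.

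**3. Size for one participant**

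Difference between the fills = highest − last. It is never negative, and it is zero when the last score is the highest.

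Illustration with assumed scores: baseline 20; hours 1 to 4 = 30, 55, 70, 45; stop after hour 4.

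- Highest score: hours 5 to 8 = 70. Change at hour 8 = 70 − 20 = +50 mm. Mean change = (200 + 4 × 70)/8 − 20 = +40.0 mm.
- Last observation: hours 5 to 8 = 45. Change at hour 8 = 45 − 20 = +25 mm. Mean change = (200 + 4 × 45)/8 − 20 = +27.5 mm.

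**4. Size for an arm mean**

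No figure in the plan depends on the fill-in rule, so there is none to reproduce. Inputs from section 4.4: 20 per arm, target 15 mm, SD 12.8 mm. Assumed: k = 1 to 3 participants in one arm, and a gap D (highest − last) of 10 to 40 mm.

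- Fully imputed time point: shift = k × D/20. Smallest 1 × 10/20 = 0.5 mm; largest 3 × 40/20 = 6.0 mm, and 6.0/15 = 40% of the target.
- 8-hour mean with 4 hours imputed: shift = k × D/20 × 4/8, giving 0.25 to 3.0 mm; 3.0/15 = 20%.
- Expectancy main effect in the section 9.1 model, which pools two arms (40 per level): a shift in one arm is halved, to 0.25 to 3.0 mm and 0.125 to 1.5 mm respectively.

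For scale, the standard error of a two-arm difference at the planned SD is 12.8 × √(2/20) = 4.05 mm. One participant with D = 40 mm moves a fully imputed contrast by 2.0 mm, about half a standard error.

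**5. Withdrawal before eating**

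Section 3.2 puts the baseline rating at 8.00, disclosure of the group at about 8.15 and breakfast at 8.30. Before eating, baseline is the only scheduled rating, so highest = last = baseline. Both rules record zero change, and D = 0.

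**The case against.** The best defence is that the sections address different events: 5.3 covers stopping the bread while staying in the study, and 7.5 covers leaving it. On that reading, with the 7.5 wording taken to mean days 2 and 3, only section 5.3 fills the test-day hours and the primary outcome has one rule. This narrows the point but does not remove it. The overlap case remains, the conflict on days 2 and 3 remains, and a participant who withdraws without going through the 5.3 route has no rule for the test-day hours.

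The size can fairly be called small. The protocol expects no dropouts and no need for escape medication, and it expects mild symptoms. A last rating taken just before stopping for intolerable symptoms is likely to be near the peak, so D may be close to zero. The 6.0 mm figure needs 15% of one arm to stop and a 40 mm fall from the peak before stopping. No text supports either input.

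A reader might also infer three stronger things:

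- **The primary outcome necessarily depends on which section is followed.** It may not, for the reasons above.
- **Withdrawal before eating shows the conflict.** It does not, because both rules return the baseline. It shows a weakness they share: a reaction to the information alone is scored as no change.
- **The rule will be chosen after the data are seen.** An analysis plan not at hand may settle it. The protocol alone does not.

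**Conclusion.** The contradiction stands in limited form. Two stated rules apply to a participant who stops the bread and withdraws on the test day for intolerable symptoms. The filled-in scores can differ, by highest minus last, and are equal whenever the last score is the highest. The effect is certain in the text for days 2 and 3, and conditional for the 8-hour primary outcome on how the 7.5 wording is read.

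The sizes in the working are illustrations that rest on the assumed k and D. Their upper ends are extreme cases and should not be read as expected bias. With 20 per arm they are large enough to settle the rule in advance, but they do not show that the primary result is compromised. This is a point that should be fixed, with high confidence in the inconsistency and much less in any effect on the primary result.

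**What to change.** Reconcile sections 5.3, 7.5 and 7.6 into one imputation rule, fixed before the data are seen. It should state its trigger (stopping the bread, leaving the study, or either) and the time points it covers, including the rest of the test day and the end-of-day-1 questionnaire.

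1. Ask participants who stop or withdraw to keep completing the e-diary if they are willing, and analyse the scores they give. Say explicitly that recorded scores are not overwritten. This is also the only step that helps with withdrawal before eating.
2. Where test-day scores are still missing because of intolerable symptoms, name one of the two existing rules as primary and report the other as a sensitivity analysis. Which is primary is partly a matter of choice. The highest-score rule always fills in a value at least as large, so it can enlarge the hypothesised effect if participants told they receive gluten stop more often. State this beside the choice.
3. Do not carry a test-day score into days 2 and 3. Analyse those questionnaires as observed.

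The cost is a wording change in three sections, notified to the ethics committee as an amendment, one extra sensitivity analysis, and voluntary diary entries in a system already in place. Sample size, bread, visits and the decision to stop are unchanged, as is the right to leave without giving a reason.

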6. INVESTIGATIONAL PRODUCT

6.1 Name and description of investigational product(s)

For this randomized, double-blind, controlled trial two different types of bread will be manufactured by the European Bakery Innovation Centre (Papendrecht, The Netherlands), *i.e.* gluten-free oat bread and gluten-containing oat bread. Both breads will be made using the same baker's oat flour and are prepared using food-grade ingredients suitable for human consumption. The gluten-free oat bread will be baked under gluten-free conditions. The gluten-containing oat-bread consists of oat flour with gluten as additive (see also product information sheet, D2). The amount of added gluten does not exceed the amount of gluten in commercially available bread (*i.e.* 9.3%, resulting in about 4g of gluten per slice). The baking process has been optimised so that both breads are similar with regard to texture, taste and appearance (see Figure 4), confirmed with preliminary testing in 10 healthy volunteers. The nutrient composition of the study bread has been analysed by European Bakery Innovation Centre (Papendrecht, The Netherlands), see Table 1.

Table 1. Nutritional composition of the study breads per slice of bread

Nutrient composition	Gluten-free oatbread	Gluten-containing oatbread
per portion (46 gram)		
Energy (kJ)	435.6	433.6
Energy (kcal)	103.3	101.4
Gluten (g), (%)	0.0 (0.0)	4 (9.3)
Total Protein (g)	3.1	6.8
Animal protein (g)	0.0	0.0
Plant protein (g)	3.1	6.8
Total Fat (g)	1.7	1.4
Saturated fat (g)	0.2	0.2
Monosaturated fatty acids (g)	0.8	0.7
Polysaturated fatty acids (g)	0.6	0.5
Linoleic acid (g)	0.1	0.1
Carbohydrates (g)	18.0	14.1
Mono/disaccharides (g)	1.1	0.9
Polysaccharides (g)	16.4	13.2
Dietary fibre (g)	3.0	2.5
NaCl (g)	0.6	0.4

There are no known health risks concerning the consumption of these study breads, as all products will be made with ingredients that are commercially available on the market. The

risk of consuming gluten for 1 day is considered to be very low, especially considering the fact that coeliac patients are excluded.

[figure not shown]

Figure 4. Study breads. 1. Gluten-free oat bread, 2. Gluten-containing oat bread

6.2 Summary of findings from non-clinical studies Not applicable.

6.3 Summary of findings from clinical studies

The biological feasibility of gluten inducing symptoms would be greatly enhanced if mechanisms could be defined. However, the aetiology of NCGS is under debate, since clear biological mechanisms of action and specific biomarkers are lacking (20). So far, studies examining the contribution of consumer perceptions and expectation in symptom development are scarce. A well-designed placebo controlled, cross-over study of Biesiekierski *et al.* (2013) (17), found no evidence of specific or dose-dependent effects of gluten in patients with NCGS placed diets low in FODMAPs. Overall symptoms and pain significantly worsened compared with mean scores during the last week of each dietary treatment period, irrespective of the diet (*i.e.* placebo, low-gluten or high-gluten diet). Furthermore, it is striking that the symptom scores were highest with the first treatment they received, pointing to a nocebo effect and indicating that a strong anticipatory symptomatic response was present independently of the nature of the challenge protein.

These findings indicate that a negative expectation (*i.e.* nocebo effect) and psychological factors may play a role in the experience of symptoms. Based on this study we hypothesize

that the effects of gluten or wheat bread are conditional on believing that one has or has not consumed gluten-containing foods. So, by telling self-reported gluten sensitive people that they will be eating study bread containing gluten, they may experience gluten induced GI-symptoms, irrespective of the actual bread composition.

6.4 Summary of known and potential risks and benefits

The study oat breads are commercially available. Bread itself is a harmless food product, which is widely consumed on a daily basis by the general population worldwide. The volunteers may or may not experience mild GI symptoms after the consumption of the study bread, since the included participants suffer from self-reported gluten sensitivity. It should be noted that the consumption of gluten by non-coeliac gluten sensitive participants does not lead to coeliac-specific antibodies and villous atrophy or any allergy related processes (21). Typically, symptoms improve or disappear shortly (mostly within hours) after gluten is withdrawn from the diet (14, 22). The provided study breads contain no more gluten than is present in normal commercially available bread (9.3%) consuming 4 slices of the study bread will not exceed the average amount of gluten that is normally consumed per day (23). Participating in this study does not lead to direct benefits for the individual participants, but may give the participants some insights into the effects of gluten and wheat on their symptoms and well-being. The results of this study will be used to better understand why some types of bread can lead to certain symptoms and who is most vulnerable to experience these symptoms.

Although the risk of consuming gluten for 1 day is considered to be very low, we still would like to limit any potential risk by excluding participants with coeliac disease. Furthermore, the inclusion of such patients may lead to a bias in the study and the expected effects. Therefore, volunteers will only be eligible when coeliac disease is ruled out by means of serologic examination or previous upper GI endoscopy. Participants reporting wheat allergy during the screening visit will also be excluded.

6.5 Description and justification of route of administration and dosage

Participants are requested to consume the study breads during one day: *i.e.* 2 slices for breakfast and 2 slices for lunch (for more details see section 3.2).

6.6 Dosages, dosage modifications and method of administration

When baseline measurements are completed, participants will start the intake of the provided study bread during the test day for breakfast and lunch, i.e. gluten-free oat bread

or gluten-containing oat bread (containing 9.3% gluten) made from 100% food-grade ingredients suitable for human consumption. Participants will be asked to consume 4 slices of study bread that day, *i.e.* 2 slices for breakfast and 2 slices for lunch with the choice to prepare their bread meal with margarine plus cheese, cooked ham or jam (one standardised portion of one topping per slice, all gluten-free). It is important that this is the only dietary change the participants make during the test day. For more detailed information, see paragraph 3.2.

6.7 Preparation and labelling of the Intervention Product

Study bread products will be packed and labelled at European Bakery Innovation Centre, Papendrecht, The Netherlands. Blinding is ensured by the fact that the study breads are similar in texture, taste, and appearance, confirmed with preliminary testing in 15 healthy volunteers. Frozen packages of daily bread portions for the test day will be provided with a label that refers to the "expectancy" arm only, thus the actual treatment alignment is blinded for both the participants and researcher(s).

The packages will contain the following information:

- Study name (WoW study)
- Subject code ("WOW{000}").
- Packing date (e.g. 04-12-2017)
- Expiration date (e.g. 08-12-2019)

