3.2 Test day (Day 1)

On the test day, upon arrival in MUMC+, Amsterdam UMC or WUR, the participants will be informed by the researcher(s) that they have been allocated to a specific group (*i.e.* E+ or E-). They will then receive either gluten-containing (G+) or gluten-free (G-) oat bread. The participant and the investigator will both be blind to the actual study intervention the participant will receive, *i.e.* the gluten-containing (G+) or gluten-free bread (G-) within each of the expectancy groups (See Figure 2).

This randomization results in 4 groups:

Group 1: Participants with the expectation of receiving gluten-free bread but actually receiving gluten-containing bread during the test day (E-, G+).

Group 2: Participants with the expectation of receiving gluten-free bread and actually receiving gluten-free bread during the test day (E-, G-).

Group 3: Participants with the expectation of receiving gluten-containing bread and actually receiving gluten-containing bread during the test day (E+, G+).

Group 4: Participants with the expectation of receiving gluten-containing bread but actually receiving gluten-free bread during the test day (E+, G-).

During the test day, participants are asked to come to the MUMC+, Amsterdam UMC or WUR in a fasted state at 8.00AM. Before the participants are informed about which group they are assigned to, they will first have to fill in the symptom questionnaire and the positive and negative affective scale (PANAS) as baseline measurements. Then (± 8.15 AM) they will be informed that they have been allocated to the gluten-containing or gluten–free groups (i.e. creating expectancy, E- or E+) and at 8.30AM they have to consume 2 slices of study bread for breakfast and at 12.30PM a further 2 slices for lunch. All slices can be prepared with margarine plus cooked ham, or cheese, or marmalade (one standardised portion of one topping per slice, all gluten-free). Furthermore, they will be allowed to drink coffee, tea or water (ad libitum) during the test day. Other foods or drinks are not permitted during the test day until 4.30PM. During the test day, the participants are free to do what they want to (watching TV, reading, working, possibly take a walk), provided that they complete the questionnaires every hour.

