Frozen packages of bread portions for the test day will be provided by European Bakery Innovation Centre, Papendrecht, The Netherlands, with a label that refers to the "expectancy" arm, but the actual treatment is blinded. Participants will be asked to report their GI symptoms, extra-intestinal symptoms, stool characteristics, and the PANAS in an electronic diary at baseline (at 8.00AM) and every hour till 4.30PM. After 4.30PM, participants will go home and will be allowed to eat freely as normal. During the study visits and telephonic contacts, the presence of serious adverse events will be checked. Participants will also be instructed to contact the researcher if their health status changes.

If participants are unable to stay at the MUMC+, Amsterdam UMC or WUR the entire day, they will receive the breakfast and the baseline questionnaire at the study location and can do the follow-up (*i.e.* completing the hourly questionnaire and consuming the study lunch) at home or at work, provided that all hourly questionnaires will be completed on the same tablet or notebook. If necessary, a study tablet will be provided for the test day. Subjects will receive a text message 5 minutes before each timepoint they have to fill in a questionnaire and will be informed that time of completion will be logged. Furthermore, participants have to adhere to the dietary restrictions. If possible, participants consume the study lunch in the presence of the researcher. Alternatively, participants are asked to provide pictures as proof of completely consuming the study lunch. The starting time of the test day can be flexible (before 9.00AM) and results in a shift of all time points, therefore it does not affect the structure of the test day. Any alterations in the test day (e.g. location of completing the hourly questionnaires) will be logged and taken into account during analyses.

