6.8 Study bread accountability

The study breads will be shipped by delivery courier to the MUMC+. Products will be labelled according to the randomization scheme, see paragraph 7.2. The products will be preserved in the freezer with a temperature of -18°C until needed at the central kitchen of the MUMC+, this freezer is only used to store food products. Participants will consume 2 slices study breads for breakfast and 2 slices for lunch.

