7.2 Randomisation, blinding and treatment allocation

After screening and subsequent inclusion in the study, each participant will be assigned to a unique participant identifier code. Participants will be randomly assigned to one of the following experimental conditions:

- 1. Gluten-free expectation and actually receiving gluten-free oat bread (E-, G-).
- 2. Gluten-free expectation but actually receiving gluten-containing oat bread (E-, G+).
- 3. Gluten-containing expectation but actually receiving gluten-free oat bread (E+, G-).
- 4. Gluten-containing expectation and actually receiving gluten-containing oat bread (E+, G+).

The randomisation lists will be generated by an independent co-worker from the same department as the principal investigator who is not further involved in the study, using a publicly available procedure through the internet (http://randomizer.org). This random number generator performs balanced permutations, resulting in an equal number of participants per treatment order followed. Participants will be randomly allocated to the treatment conditions and there will be a stratification on gender using block randomisation (block sizes of 8). The randomisation scheme will be up to n=90, this to be sure in case of dropouts, to randomize potential (new) participants to a new randomization number.

The investigator has no access to the randomisation list that conceals the intervention code. However, since expectation may play a role in the experience of symptoms, the investigator is unblinded to the expectation arm since the investigator has to inform the participant about allocation to the gluten-free or gluten-containing expectation group. Of course, the investigator is blinded to the actual treatment. The randomisation list will be kept in a sealed envelope by the head of the department (prof. dr. [name]), to reveal the treatment in case of medical emergency. Primary investigators of all participating centres will receive the contact details of prof. dr. [name]. The condition numbers as allocated by the independent colleague, who will carry out the randomisation, are registered by the investigator in the screening and enrolment log. Furthermore, the same co-worker will keep the randomisation lists. The "randomization key" will be provided to the investigator only after all experimental and statistical procedures have been completed.

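### The pack label refers to the expectancy arm, so concealment of the primary randomised factor from staff before inclusion and before baseline is not assured

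*Protocol*

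**What the plan says.** - **Label.** Protocol 6.7 says packs are "provided with a label that refers to the 'expectancy' arm only, thus the actual treatment alignment is blinded". Section 3.2 repeats this: packs come "with a label that refers to the 'expectancy' arm, but the actual treatment is blinded".
- **Itemised contents.** Section 6.7 then gives a list under "The packages will contain the following information". It has four items: study name, subject code, packing date and expiration date. The expectancy arm is not among them.
- **When and how labelled.** "Study bread products will be packed and labelled at European Bakery Innovation Centre, Papendrecht, The Netherlands" (6.7). Section 6.8 adds "Products will be labelled according to the randomization scheme, see paragraph 7.2" and keeps the packs in a freezer at the MUMC+ central kitchen until they are needed.
- **Codes and allocation.** Section 7.2 states: "After screening and subsequent inclusion in the study, each participant will be assigned to a unique participant identifier code". It goes straight on to random assignment to the four conditions. The list of study steps in section 3 instead puts randomisation and treatment allocation on the test day.
- **Who knows what.** Under 7.2 the investigator has no access to the list that conceals the intervention code and is blind to the bread. The investigator does know the expectation arm, and the reason given is that he or she must tell the participant.
- **Test-day order.** "Before the participants are informed about which group they are assigned to, they will first have to fill in the symptom questionnaire" (3.2). Baseline is at 8.00AM, disclosure at about 8.15AM and the first bread at 8.30AM.
- **Primary question.** Section 2 defines it as E+G- against E-G-.

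**The concern.** Concealment before allocation and blinding after it are separate safeguards. This trial must give up the second for the expectancy factor, because someone has to deliver the message. It does not have to give up the first. Yet the label is designed to hide the bread, which is the secondary factor, and it refers to the arm of the primary one.

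A pack that shows both a subject code and an expectancy arm links code to assignment. If staff who screen, schedule or receive participants can see that link, two things become possible. Whether and when a person is booked could depend on the arm that is coming. Staff could also give unintended cues before baseline is recorded. The outcome is a self-reported VAS score, the intervention is verbal, and there are 20 participants per group, so the comparison is sensitive to either.

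Section 7.5 adds a related weakness. Participants who withdraw after consent but before the test day may be replaced, and their results are destroyed when the study is completed. If the arm could be known in that interval, withdrawal related to the arm would be hard to check afterwards.

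**Working it through.** The protocol gives no figure on this point, so there is none to reproduce. The check compares the sections and then sets out how predictable the arm would be.

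**1. Is the expectancy arm on the pack?** The narrative sentences in 3.2 and 6.7 say the label refers to it. The four-item list in 6.7 leaves it out. Both cannot be a full description of the label. If the narrative governs, the arm is readable. If the list governs, it is not.

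**2. Is the label applied before the test day?** Yes. Labelling is done at the bakery (6.7) from the randomisation scheme, and the packs are then shipped by courier and stored at -18°C (6.8). The example dates in 6.7 (packed 04-12-2017, expiring 08-12-2019) are two years apart, so long storage is possible. The protocol does not say that the whole stock is made at once.

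**3. Does any stated safeguard cover the expectancy arm?** No.
- The blinding statements in 3.2 and 6.7 concern the actual bread.
- The withheld list in 7.2 is described as concealing the intervention code.
- The reason in 7.2 for the investigator knowing the expectancy arm is the duty to inform. Under 3.2 that duty arises at about 8.15AM, after baseline. It gives no reason for earlier access.

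**4. When is allocation made?** Section 3 says on the test day. Section 7.2 describes codes and random assignment following inclusion, and has the investigator enter condition numbers in the screening and enrolment log. What those numbers reveal is not stated. The interval in which the arm could be known is therefore undefined.

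**5. How predictable would the next expectancy arm be?** Section 7.2 gives blocks of 8 over four conditions, stratified by gender. If balanced, each block holds n = 4 E+ and n = 4 E-. Assume a person knows all past expectancy assignments in the stratum and always guesses the arm with more places left. The expected number of correct guesses per block is

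n + 2^(2n-1)/C(2n,n) - 1/2 = 4 + 128/70 - 0.5 = 5.33 of 8, or 66.6%.

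| What is known | Correct guesses of next arm |
|---|---|
| Nothing | 50% |
| Past expectancy assignments and the block size | 66.6% |
| The label and which pack is next | 100% |

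The last row applies only if the label is readable, the person has access to the stock and the next code is known. The label issue is separate from block size: it would remain under any block size, and the 66.6% would remain after the label is changed.

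**The case against.** The strongest reply is that the leak is not shown to happen.

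- Section 7.2 gives allocation to an independent colleague, and the investigator only registers the condition number.
- The pack code in 6.7 has the form WOW{000}, while 11.1 gives participant codes by site in another form (for example MUMC.S00xx). Holding a participant code at inclusion need not reveal which pack will be used.
- The stock is in one hospital kitchen, while recruitment also runs at Amsterdam UMC and WUR.
- The four-item list may be the true label.
- Baseline is self-reported by a participant who has not yet been told the arm and will be told about 15 minutes later. The investigator then openly knows the arm for the rest of the day.

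Most of this stands, and it limits the claim. A reader might infer that anyone handling the stock can read upcoming assignments before enrolment, or that the same staff screen, give out codes and run baseline. The documents do not say so. That reading needs packs labelled well ahead, codes used in a known order within gender, and recruiters with access to the freezer, and none of these is stated.

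A reader might also try to size the bias by supposing that a few participants are exchanged between E+G- and E-G-. The documents do not support this either. Staff are blind to the bread and cannot target those two cells, and there is no basis for any exchange rate or difference in reactivity. Even the direction is open: an early cue that raised baseline scores in E+ would shrink the change from baseline in that arm.

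The reply does not remove the gap. An independent allocator conceals nothing that is also shown on the pack, and no section describes hiding the expectancy arm from staff before inclusion or baseline.

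**Conclusion.** The point holds as a lack of assurance, not as a demonstrated leak. The protocol twice says that subject-coded packs, labelled in advance from the randomisation scheme, refer to the expectancy arm. Every stated safeguard concerns the other factor. Concealment of E+ against E- from staff before inclusion and before the 8.00AM baseline is therefore not assured.

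Two inconsistencies add to this: the label sentence against the label list within 6.7, and section 3 against 7.2 on the timing of allocation.

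The effect on the estimated difference cannot be derived, because access to the stock and knowledge of the next code are not stated. Only predictability can be bounded: 50% by chance, 66.6% from the blocks under the assumptions shown, and 100% if label and next pack are both known. The change is worth making because the exposed factor is the primary one, the outcome is subjective, and the remedy is cheap.

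**What to change.** - **3.2 and 6.7:** remove the reference to the expectancy arm from the pack label and keep only the four items already listed (study name, subject code, packing date, expiration date). This also settles the conflict within 6.7.
- **7.2:** have the independent co-worker supply E+ or E- separately, by opaque numbered envelope or through the electronic system already used for questionnaires. It should be released to the investigator only after the baseline questionnaires are saved on the test day. The bread code stays concealed as now.
- **Section 3 and 7.2:** state one time for randomisation and one for disclosure to staff, and say that the condition number in the enrolment log does not reveal the expectancy arm.
- **If a visible label is wanted as part of the manipulation:** attach it after baseline is saved.

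The cost is new label wording, a set of envelopes or a system setting, and one extra step for staff on the test-day morning. Sample size, outcomes and analysis do not change.
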